titration rates. The design provides robust statistical strength and controls for selection bias created by individual variability in cognitive performance. The use of healthy subjects will control for the effects of epilepsy, underlying brain dysfunction, and changes in seizure frequency on cognitive function. In addition, examining ASM cognitive effects in healthy subjects allows extrapolation of the results to other patient populations that might be potentially treated with ASMs (e.g., tremor, pain). We have conducted multiple studies with similar design with an excellent safety record that have provided clear delineation of the cognitive side effects of ASMs ([name], et al. 2019).

II. STUDY QUESTIONS

1. What are the behavioral, cognitive or other side effects of perampanel at different titration rates in healthy volunteers?
2. What is the time course of habituation to objective vs. subjective neuropsychological (e.g., cognitive and behavioral) side effects of perampanel?

III. STUDY OBJECTIVE

The objective of this study is to determine whether there are any differences in the cognitive abilities and/or behavioral response of normal healthy volunteers across different titration rates of perampanel.

IV. STUDY DESIGN

The study will employ a randomized, double-blind, parallel group design across different titration rates of perampanel in healthy volunteers. Every subject will be treated with perampanel (PER) at one of four different titration rates: (1) 2mg/day PER for one week followed by 4mg/day PER for five weeks, (2) 2mg/day PER for two weeks followed by 4mg/day PER for four weeks, (3) 4mg/day PER for six weeks, or (4) placebo (0mg/day PER) for six weeks. A study physician will monitor each subject during ASM treatment period. Subjects will undergo cognitive, behavioral, and safety testing at screening, prior to initiation of the first dose, and at the end of each week during the titration and maintenance period. Subjects and study personnel in direct contact with subjects will be blinded to ASM treatment.

V. STUDY POPULATION

A. Number and type of subjects

Healthy males and females between the ages of 18 and 55 who do not require concomitant medications that affect study medications or cognitive and behavioral functions. One hundred and three subjects across three academic medical centers (Stanford University, New York University, and Northwestern University) will be enrolled in the study in order to complete 76 subjects.

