PER ^b -3			4mg	4mg	4mg	4mg	4mg	4mg
Partial NP ^c			X	X		X	X	
Full NP ^d	X	X			X			X
TEAEs ^e	X	X	X	X	X	X	X	X

Testing is at the end of each week.

^aBL = baseline visit.

^bPER = perampanel.

^cPartial NP = partial neuropsychological battery on non-clinic visit weeks refers to online CNS-Vital Signs computerized cognitive tests and behavioral questionnaires (POMS-total, AEP, & QOLIE-89 cognitive scores, which will be mailed back).

^dFull NP = full neuropsychological battery includes Non-computerized cognitive tests and the Partial NP (questionnaires and online CNS-Vital Signs computer tests).

^eTEAEs = treatment emergent adverse events.

The investigative team will monitor each subject's progress and safety during ASM treatment periods. Subjects will remain in their treatment arm for a total of 6 weeks.

D. Enrollment Goals

Previous studies indicate that an enrollment of 103 subjects will be required to obtain 76 evaluable subjects. See Statistical Section for power analysis.

E. Visit-Specific Treatment and Evaluation Sequence

Subjects will be randomly assigned to one of four possible titration schedules. Each titration schedule lasts 6 weeks.

At all visits, subjects will be advised on drug compliance and avoidance of medications which may adversely effect the results of cognitive function testing. Adverse events will be documented on the appropriate case report form. Appointments will be made for follow up visits and care will be taken to schedule all cognitive and behavioral function testing for a given subject at the same time of the day. Dosing of the study medication should be at approximately the same time of day (e.g., before the participant goes to sleep). However, due to the long half-life of perampanel, this is not critical. The time of testing and time of last 2 doses will be recorded.

The timetable for the study is listed in Appendix A. This is a visit-by-visit description of the events scheduled for each visit.

Visit 1 Screening Visit (-1 weeks prior to randomization)

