ANY MEDICALLY SERIOUS ADVERSE EVENT REQUIRES IMMEDIATE NOTIFICATION OF THE FDA BY THE INVESTIGATOR.

Any serious adverse event that occurs up to two weeks following study participation must also be reported.

Serious adverse events must be reported to the lead site principal investigator, [name], within 24 hours of the site becoming award of the SAE.

Serious adverse events must be reported to sites' institutional review boards (IRB) according to their IRB's regulations.

Specific procedures for Double-Blind Studies

Site personnel not involved in direct care of study subjects will generate a randomization code. In an acute medical emergency, the randomization code may be broken if this is considered essential for subject management. For this purpose, the sealed randomization code will be provided to the investigator by the site pharmacy. If the code is broken, a record of the date, time and reason must be put into writing and sent to Eisai. This letter will become part of the permanent study record.

All adverse events should be recorded on the appropriate Case Report Forms (CRF's) including date of onset and cessation, intensity and relationship to study drug. The action taken and clinical outcome of the adverse event will also be recorded.

The investigator will report all serious AE's to the FDA and to Eisai without delay.

D. Medication Compliance Assessment

Compliance is to be judged by questioning the patient at the clinic visit and by the non-blinded observer's inspection of medication returned and recording missed doses on the appropriate CRF. Repeated noncompliance, or the missing of all scheduled doses of medication for three (3) consecutive days (72-hour period) would be cause for removing the subject from the study. Subjects should take all doses for 3 days before visits when cognitive function testing occurs.

E. Subject Discontinuation Criteria

1. Although they may withdraw without prejudice at any time, every effort should be made to have subjects complete the study within the bounds of safety and provisions of informed consent.
2. The investigator may discontinue the participation of any subject in this study if:
 - a. Any clinically significant adverse experiences are observed.
 - b. The subject is grossly noncompliant.
 - c. The subject's health would be jeopardized by continued participation.

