 - d. Consent is withdrawn. Subjects will be encouraged to complete the study, although they may withdraw at any time without prejudice.
4. Subject replacement.

Subjects who are dropped from the study prior to completion of all cognitive testing will not be replaced.

Subjects who are withdrawn prior to completion of at least one set of cognitive testing on treatment drug (i.e., prior to visit 5/study week 3) may be replaced.

5. Follow-up of discontinued patients

Subjects who receive study drug and are discontinued from the study will have all safety assessments completed, including a complete physical examination and laboratory evaluation including chemistry, hematology with differential, urinalysis and urine pregnancy test as required at study termination. This testing should be done as soon as possible. Medical follow-up of any severe adverse events or clinically significant abnormal laboratory values will continue until the abnormality resolves, and adequate medical explanation is apparent. Such data will be provided to Eisai.

X. STATISTICAL EVALUATION

A. Sample Size

We assume that the 4 groups (3 PER treatments and a placebo group) are equally spaced (in terms of z-score) at the time point of maximum drug effects (end week 1 for 4mg group and end week 3 for titration to 2mg x2wks then 4mg group), with a maximum difference of 0.24 (which is the difference between the placebo group and treatment at max effect). We then assume that over the 4 visits after max drug effect the z-scores get closer together until

they are equal at the treatment week 6th. The calculation indicates that at least 18 subjects are needed in each group to have 80% power. Since there are 4 groups, the total sample at least finishing assessment at end of week 6 (event 8) would be $19 \times 4 = 76$. Enrollment will include 20% (n=15) more to account for dropouts prior to assessment at end of visit 2 (baseline), and ~15% (n=12) more for dropouts before end of event 8 (treatment week 6). Thus, the total enrollment sample will be 103 subjects.

In summary, the 4 total groups (3 PER treatment, 1 placebo) would need at least 19 subjects per group (76 total), and total enrollment would be rounded to 105 to account for dropouts.

B. Methodology for statistical analysis

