The parameters of interest are listed in Section VII. Descriptive statistics will be used to provide an overview of the primary, secondary, and other variable results. For categorical parameters, the number and percentage of subjects in each category will be presented. The denominator for percentages will be based on the number of subjects appropriate for the purpose of analysis. For continuous parameters, descriptive statistics will include number of subjects, mean, standard deviation (SD), median, minimum, and maximum. Unless otherwise specified, baseline neuropsychological data will be based on the Visit 2 assessments.

Study question 1: What are the behavioral, cognitive or other side effects of perampanel at different titration rates in healthy volunteers?

The primary outcome variable will be the overall neuropsychological composite z-scores for the objective and subjective measures combined.

Study question 2: What is the time course of habituation to objective vs. subjective neuropsychological (e.g., cognitive and behavioral) side effects of perampanel?

The primary outcome variable will be the neuropsychological composite z-scores for the objective and subjective measures, which will be analyzed separately.

The objective measure z-score will be calculated by averaging overall computerized and noncomputerized cognitive z scores, which are calculated by averaging individual z-scores of selected performance measures from the computerized cognitive test battery (i.e., average of z-scores for the domain scores for executive function and for processing speed) and from the noncomputerized cognitive test battery (i.e., average of individual z-scores for MCG immediate, MCG delayed, SDMT, and Stroop-average score). The subjective measure z-score will be calculated by averaging the individual z-scores for AEP, POMS, and QOLIE-cognitive questions (average of 3 scores from QOLIE). These z-scores will be assessed by a 4 (titration rate) \times 6 (time: weeks 1-6) ANCOVA controlling for scores at Baseline (visit 2) using an intent-to-treat analysis for those receiving neuropsychological testing at least at the end of week one. Imputations will be employed for dropout after week one.

We will control for differences across groups in age, gender, and personal/family history of psychiatric disorders.

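### Three centres recruit and site staff generate the randomization code, but the primary ANCOVA has no site term: adding one is a cheap improvement

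*Combined protocol and SAP*

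**What the plan says.** Section V.A plans "One hundred and three subjects across three academic medical centers". On allocation, VI.E says only this: "Subjects will be randomly assigned to one of four possible titration schedules". The one statement on how the code is produced is in IX.C, under the procedures for double-blind studies: "Site personnel not involved in direct care of study subjects will generate a randomization code". The same paragraph, which deals with emergency unblinding, adds that "the sealed randomization code will be provided to the investigator by the site pharmacy". No section mentions strata, block size, or whether there is one list or one per centre.

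For the primary analysis, X.B specifies a titration-by-week "ANCOVA controlling for scores at Baseline (visit 2) using an intent-to-treat analysis" and then says: "We will control for differences across groups in age, gender, and personal/family history of psychiatric disorders". Site is in neither the model nor the covariate list. The sample size section (X.A) gives no site variance.

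**The concern.** When randomization is balanced within a factor, the analysis should normally contain that factor. Balancing removes the factor from the differences between arms. If the model omits it, its variance stays in the error term, and the standard error is then too large for the design that was used.

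Generation and custody of the code at site level make within-site lists a natural reading. Sites could also differ on the outcome. The MCG paragraphs, SDMT and Stroop are given face to face at clinic visits, so by different staff at each centre, and they enter the objective score.

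At stake is sensitivity. The trial looks for cognitive and behavioural side effects, so a needlessly conservative test makes a real effect harder to detect.

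**Working it through.** **1. The plan's own figure.** X.A assumes four equally spaced groups "with a maximum difference of 0.24", 18 per group and 80% power. It gives no SD or within-subject correlation, so 18 cannot be reproduced. It can only be inverted. With means 0, 0.08, 0.16 and 0.24, the squared deviations from 0.12 sum to 0.0144 + 0.0016 + 0.0016 + 0.0144 = 0.032. For a one-way F test at 0.05 (assumed for the primary test), the noncentrality is n × 0.032 / SD². At n = 18, 80% power requires SD = 0.223 (noncentrality 0.576 / 0.0499 = 11.55). With 19 per group (19 × 4 = 76) the same SD gives about 82.4%. I use 0.223 as the residual SD after baseline adjustment, so that the comparison starts at the plan's stated power. It is not a documented value.

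**2. Why omission is conservative under within-site balance.** Let a share r of the residual variance lie between sites. With site omitted, the error mean square has expectation (within-site variance) + k × (between-site variance), where k = (N − Σn²/N) / 72. For assumed site sizes 28/24/24, Σn² = 784 + 576 + 576 = 1936, so k = (76 − 25.47) / 72 = 0.70. The error term is inflated by the factor 1 + 0.70 × r/(1 − r):
- r = 0.05: 1.037
- r = 0.10: 1.078
- r = 0.20: 1.175

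The 5% critical value of F on 3 and 72 df is 2.73. Multiplying it by these factors gives tail areas of about 4.4%, 3.9% and 2.8%. This is a hand check on the simulation below.

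**3. Simulation.** 76 subjects, four arms, three sites of 28/24/24, normal site effects, one between-subject score per subject, and 40,000 data sets per cell. Allocation was either permuted blocks within site or a single balanced list that ignores site. Monte Carlo error is about 0.1 point for type I error and 0.2 for power. Each entry is site omitted / site included.

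| Site share | Blocked: type I % | Blocked: power % | Unstratified: type I % | Unstratified: power % |
|---|---|---|---|---|
| 0 | 5.0 / 5.0 | 82.4 / 82.3 | 5.1 / 5.2 | 82.4 / 81.2 |
| 0.02 | 4.8 / 4.9 | 82.6 / 83.1 | 5.1 / 5.1 | 82.6 / 81.8 |
| 0.05 | 4.5 / 4.9 | 83.1 / 84.5 | 5.1 / 5.0 | 83.2 / 83.5 |
| 0.10 | 4.0 / 5.0 | 83.9 / 86.6 | 5.2 / 5.1 | 83.7 / 85.5 |
| 0.20 | 3.1 / 4.9 | 85.4 / 90.5 | 5.0 / 4.9 | 85.3 / 89.7 |

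Site sizes of 44/16/16 give nearly the same results (blocked type I error with site omitted: 4.3%, 4.0% and 3.2% at shares 0.05, 0.10 and 0.20). Holding site effects fixed at the stated share, with 6 subjects per arm-site cell, is somewhat more severe: 4.2%, 3.4% and 2.0%.

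**4. Titration-by-time.** If the site effect is the same every week, it drops out when a subject's weekly score is compared with that subject's own mean over weeks. The interaction contrast, which addresses habituation, is therefore largely untouched. The figures above concern the between-group titration test.

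**The case against.** The strongest reply is that the documents never say allocation is balanced within site. The IX.C sentence says who makes the code, refers to a single code, and sits in a paragraph on emergency unblinding. Even one list per site would not guarantee balance. This stands, and the conservative result is therefore conditional.

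A reader might infer that the error rate is wrong under either form of allocation, or that it is inflated. Neither follows. Under unstratified allocation the ordinary standard error already covers chance site imbalance, and type I error is nominal. Under blocking the error is conservative. No scenario showed inflation beyond simulation error.

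A reader might also infer that adjusting can only help. It can cost about 1 point of power when allocation is unstratified and sites barely differ (82.4% to 81.2%).

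The residual site share may also be small. The model conditions on the Visit 2 score from the same battery, which should absorb stable differences between sites. The face-to-face tests are given on treatment only at weeks 3 and 6 and make up half of the objective score. Both points stand, and they favour the upper rows of the table. They do not show that the share is zero.

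**Conclusion.** The omission is real and the consequence is conditional and modest. With allocation balanced within site, the between-group titration test is conservative: about 4.5%, 4.0% and 3.1% instead of 5% at residual site shares of 5%, 10% and 20%, with about 1, 3 and 5 points of power forgone. With unstratified allocation, type I error is nominal. Including site then ranges from a loss of about 1 point of power at a share near zero to a gain of about 2 points at 10% and 4 to 5 at 20%.

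The conclusion rests on an assumed site share after baseline adjustment, assumed site sizes, and an SD inferred from the stated power. No false-positive risk has been shown. This is a cheap improvement to one test, not a flaw that threatens the trial's conclusions.

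**What to change.** In X.B, add site (three levels) as a fixed effect in the ANCOVA models for the composite and component z-scores, beside the covariates already named. In the randomization text, state whether the list is stratified by site. Do not require the term for the comparisons of adverse events and related dropouts: with about 19 subjects per arm, events may be too sparse to support it.

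The cost is one phrase in X.B, one sentence on randomization, two degrees of freedom, and up to about 1 point of power if sites do not differ. No new data are needed, and specifying the term in advance avoids a post hoc choice.

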Provisions for prorating payment: If perampanel levels tested at visits 5 and 8 are below detectable levels, this indicates that the participant was not complying with the protocol and they will not receive their final payment of \$400 for visit 8. Please note that this only applies to participants assigned to the three perampanel groups, not the placebo group.

VII. NEUROPSYCHOLOGICAL TESTS

A. Outline:

Note that test will be performed in the following order.

Computerized Testing Battery (CNS Vital Signs system)

- Verbal memory immediate assessment
- Visual memory immediate assessment
- Symbol digit coding assessment
- Shifting attention test
- Dual task test
- One- and two-back continuous performance test
- Verbal memory delay assessment
- Visual memory delay assessment

Non-computerized cognitive/behavioral testing

- MCG paragraph memory-immediate recall assessment
- Symbol digit modalities test
- Stroop test
- Profile of mood states (POMS) assessment
- AEP
- QOLIE-89 cognitive domains (attention/concentration, language, memory)
- MCG paragraph memory-delay recall assessment
- Columbia-Suicide Severity Rating Scale

B. Description of Individual Tests:

1. Components for computerized cognitive assessments:

The computerized cognitive assessments have been used in prior studies (see reference section for CNS Vital Signs). It consists of verbal memory immediate assessments, visual memory immediate assessments, symbol digit coding, shifting attention tasks, dual task tests, one- and two-back continuous performance tests, verbal memory delayed, and visual memory delayed. Detailed descriptions of each are below.

1a. The order of computerized testing should be as follows:

- Verbal memory immediate
 - Encoding - 30 seconds
 - Immediate recognition - 1 minute
- Visual memory immediate
 - Encoding - 30 seconds
 - Immediate recognition-1 minute
- Symbol digit coding - 2 minutes
- Shifting attention test - 2 minutes
- Dual task test - 2 minutes
- One- and two-back continuous performance test - 5 minutes
- Verbal memory delayed - 1 minute
- Visual memory delayed - 1 minute

These are actual test run times and do not include reading instructions or practice tests.

1b. Verbal memory immediate assessment:

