The incidences of all adverse events reported during the trial will be tabulated by treatment and study period. The other safety variables, which include changes in hematology, clinical chemistry, and urinalysis parameters, and vital signs will be analyzed descriptively. The actual measurement and its change from baseline will be presented by visit and period of collection. In addition, shift tables may be used to evaluate the number and percentage of subjects having a different post-baseline status when compared with their baseline status.

C. Interim Analysis

No interim analyses are planned.

D. Definition of Evaluable Subjects

Any subject who ingested one or more doses of blinded study medication and provided follow-up information will be evaluable for the analysis of the safety data. The primary analysis will include subjects who complete all visits or at least one set of cognitive/behavioral testing on treatment drug and who did not have any important deviations, which may have an impact on cognitive function. Subjects who prematurely discontinue the study will be evaluated based on the data collected at each visit attended. Any subject who is evaluable for the safety analysis who also has baseline and end of drug period cognitive/behavioral data available will be evaluable for the intent-to-treat analysis of the parameters of interest. Any subject evaluable for the intent-to-treat analysis will be evaluable for the per-protocol analysis of the parameters of interest provided that the subject was compliant with the protocol with regard to the study medication regimen, use of concomitant medications, sleep requirements prior to cognitive testing, alcohol consumption, caffeine consumption, and use of OTC medications prior to cognitive testing. All data will be used to their maximum possible extent, but without any imputations for missing data for any parameter.

XI. REFERENCES:

1. Background References.

French, J. A., Krauss, G. L., Steinhoff, B. J., Squillacote, D., Yang, H., Kumar, D., & Laurenza, A. Evaluation of adjunctive perampanel in patients with refractory partial-onset seizures: results of randomized global phase III study 305. *Epilepsia* 2013;54(1), 117-125.

Krauss, G. L., Bar, M., Biton, V., Klapper, J. A., Rektor, I., Vaiciene-Magistris, N., ... & Kumar, D. Tolerability and safety of perampanel: two randomized dose-escalation studies. *Acta Neurol Scand* 2012a;125(1):8-15.

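### Subjects removed for noncompliance get no further cognitive testing, so they leave the intent-to-treat set as X.D defines it, and the later scores needed for the habituation question are lost

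*Combined protocol and SAP*

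**What the plan says.** - **Removal (IX.D, Medication Compliance Assessment).** Repeated noncompliance is one trigger. The other is missing every dose for "three (3) consecutive days (72-hour period) would be cause for removing the subject from the study". Neither is restricted to an arm. On the evidence used: "Compliance is to be judged by questioning the patient at the clinic visit and by the non-blinded observer's inspection of medication returned".
- **Discontinuation (IX.E, item 2).** "The investigator may discontinue the participation of any subject in this study if" one of several conditions is met, including "The subject is grossly noncompliant". That threshold is not defined.
- **After discontinuation (IX.E, item 5).** The plan lists safety assessments: physical examination, laboratory tests and follow-up of abnormalities. Cognitive tests and questionnaires are not listed.
- **Analysis sets.** X.B describes an ITT analysis of those tested at least at week 1, with imputation for later dropout. X.D requires baseline and end-of-drug-period scores for ITT and rules out imputation. It also leaves subjects with important deviations that may affect cognition out of the primary analysis. Per-protocol is ITT "provided that the subject was compliant with the protocol with regard to the study medication regimen", together with other conduct rules.
- **Blinding.** Section IV: "Subjects and study personnel in direct contact with subjects will be blinded to ASM treatment". VI.B says all capsules are identical.

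**The concern.** Tolerability is what this trial measures. A volunteer who feels sleepy or unsteady on study drug may well skip capsules, so noncompliance may itself be a result of treatment. X.D already handles noncompliance by excluding such subjects from the per-protocol set. Removing them from the study as well takes away the observations that would make ITT differ from per-protocol.

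Study question 2 asks how side effects fade over time, which needs scores from every week. If the most affected subjects stop contributing partway through, the later part of the curve rests on those who tolerated the drug, and habituation can look faster or more complete than it was.

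**Working it through.** **1. The two analysis sections side by side**

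| Point | X.B | X.D |
|---|---|---|
| Who is in ITT | Tested at least at week 1 | Baseline and end-of-drug-period scores available |
| Missing scores | Imputed after week 1, method not named | No imputation for any parameter |
| Deviations | No exclusion stated | Important deviations left out of the primary analysis |
| Early discontinuation | Covered by imputation | Data from visits attended are used |

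**2. One subject traced through.** Take a subject tested at weeks 1, 2 and 3, who then misses three full days and is removed in week 4.

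- X.B: in ITT. Weeks 4, 5 and 6 (3 of 6 time points) are imputed by an unstated method.
- X.D, ITT: out, because there is no week 6 score. Per-protocol: out, because it requires ITT status.
- X.D, primary analysis: in with weeks 1 to 3, unless the missed doses count as an important deviation, in which case out.
- Under both sections the week 4 to 6 scores do not exist. X.A assumes the groups converge to equality by week 6, so these are weeks in which habituation is expected to show.

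**3. Planned loss on treatment (X.A).** The enrollment figure reproduces: 76 + 15 + 12 = 103. Leaving out the 15 lost by baseline gives 103 − 15 = 88, or 88 / 4 = 22 per arm. The on-treatment allowance is 12 / 88 = 13.6%, pooled. No split by arm or by reason is given.

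**4. Possible scale, on assumptions only.** Suppose all 12 losses are removals that leave the analysis, as under X.D's ITT definition. With a normal model, removal fraction q, score SD s, and correlation r between score and removal (the same in every arm), an arm's mean shifts by

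r × s × φ(z_q) / (1 − q).

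The bias in active versus placebo is the difference between the two arms' shifts. The documents give neither s nor r. I assume s from 0.25 to 0.5 and r from 0.2 to 0.5, so r × s runs from 0.2 × 0.25 = 0.05 to 0.5 × 0.5 = 0.25.

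- Equal removal (13.6% in every arm), or r = 0: bias 0.
- 5% placebo, 16.5% active (0.05 × 22 + 0.165 × 66 ≈ 12): factor 0.297 − 0.109 = 0.189 before rounding; bias 0.009 to 0.047 z.
- 0% placebo, 18.2% active (0.182 × 66 ≈ 12): factor 0.323; bias 0.016 to 0.081 z.

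Against the maximum difference of 0.24 z in X.A, the last two cases are 4% to 20% and 7% to 34%. This shows how the answer depends on the inputs; it is not an estimate. The 0.24 is also only a yardstick: X.A puts the peak for the immediate 4 mg arm at the end of week 1, a score that a subject removed later would already have given.

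**The case against.** The strongest defense is that the plan is softer than IX.D alone suggests. The removal wording is permissive, the investigator has discretion, and IX.E asks for every effort to have subjects complete. X.B keeps anyone tested at week 1, and X.D itself uses the visits attended. One could also read the end of the drug period as a subject's own last on-drug test. Retained off-drug scores would themselves pull the comparison toward no effect. Each of these points has weight. They mean that the move of ITT toward per-protocol follows from X.D on its natural reading, not from the whole plan. They do not restore the missing scores or settle which section governs.

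A reader might infer more, and these inferences are not supported:

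- **That the blood-level rule removes perampanel subjects selectively.** VI.F says of it: "Please note that this only applies to participants assigned to the three perampanel groups, not the placebo group". But its stated consequence is loss of the $400 Visit 8 payment, at the last visit. Nothing links a level to removal or to an analysis set, and a perampanel assay cannot show noncompliance on placebo.
- **That removal rests on the unblinded check alone.** Compliance is judged partly "by the non-blinded observer's inspection of medication returned", but questioning also counts and the decision is the investigator's.
- **That removal is known to differ by arm.** The 72-hour rule is the same for all. Unequal removal through unequal tolerability is plausible, but it is an inference.
- **That side-effect stops will be relabeled as noncompliance.** IX.E lists adverse experiences as a separate ground, and adverse events and the action taken are recorded.

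**Conclusion.** The point holds as a cheap improvement. Removal from the study with no planned cognitive follow-up, combined with contradictory ITT and imputation rules, leaves the handling of subjects who stop dosing undefined. Under X.D they leave ITT; under either section their later scores are lost.

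A bias toward tolerability is possible if skipping is related to side effects. Its presence and size cannot be established, because the documents give no removal rates by arm and no link between removal and score. The 0.009 to 0.081 z range rests wholly on assumed rates, SD and correlation, and on treating every on-treatment loss as a removal. It falls to zero if removal is equal across arms or unrelated to scores.

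The non-blinded inspection is a secondary weakness: it contributes to the compliance judgment but does not decide removal by itself.

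**What to change.** - **IX.D:** record the noncompliance and keep all remaining scheduled cognitive tests and questionnaires for subjects who still consent. Let noncompliance affect the per-protocol set only.
- **X.B and X.D:** use one ITT definition, those tested at week 1 as in X.B, without the end-of-period requirement. State that medication noncompliance is not an important deviation for the primary analysis. Without this, retained subjects could still be excluded. Choose one missing-data rule for both sections; if imputation stays, name the method.
- **IX.D and IX.E, item 2b:** reconcile the two passages on discontinuation. Whether study drug continues stays with the investigator.
- **Capsule counts:** have returned capsules counted by staff blinded to arm where pharmacy records allow. The VIII.D dispensing logs list active and placebo capsules, so full reconciliation may have to stay with the pharmacy.

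The cost is amendment wording plus visits already in the schedule. Under VI.F, the remaining payments for a subject kept on after Visit 5 are at most 100 + 100 + 400 = $600, within the $1,300 planned per subject. The statistical downside is that some low-exposure subjects slightly dilute the ITT estimate; the per-protocol analysis shows the undiluted one.
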